8.8.5 Adverse Events of Special Interest

Newly acquired skin eruptions that are non-traumatic will be considered AESIs. These may include, but are not limited to eruptions such as skin rashes, skin irritations, skin reactions, or acneiform lesions. This does not include localized contact irritation at ECG lead sites due to application/removal of lead adhesive.

Refer to the separate Rash/Skin Eruption AESI Workup Instructions for complete details, including reporting forms, on extra measures that must be performed to characterize any skin AESI of a newly acquired skin eruption that is non-traumatic.

All AESIs should be reported as IREs (see Section 8.8.3).

8.8.6 Abuse Potential Monitoring Process, Events Subject to Additional Monitoring, and Medication Handling Irregularities

An Abuse Potential Monitoring Process (APMP) will be in place and will be shared with each site. A key objective of the APMP is to monitor for instances of abuse or diversion of the trial medication and other psychoactive substances. In addition to monitoring for irregularities in medication handling, AEs that may be suggestive of a developing abuse issue will also receive special attention. As part of the APMP, MHIs must be reported, and AEs related to abuse potential and AEs involving MHIs must be reported as an ESAM with detailed narratives.

Investigators and site staff at each trial site will be trained on reporting potentially abuse related AEs (eg, recording a description of the event in the subject's own words in the source documents as well as the eCRF, in addition to the clinical term, and to be aware that a subject's report may encompass more than one event and that these should be recorded separately). The investigators will be provided with examples of potentially abuse-related AEs, and trained on how to handle such events (eg, additional monitoring). While the investigators will be provided with examples of AE terms as a guide during trial conduct, the analysis of potentially abuse-related AEs will be based on a search of all Medical Dictionary for Regulatory Activities (MedDRA) preferred terms, all verbatim terms, and any open text fields within the AE data to identify text strings suggestive of abuse potential, in line with the 2017 FDA guidance (Assessment of Abuse Potential of Drugs). Refer to the separate APMP documentation for complete details on MHIs and ESAMs, including documenting and reporting procedures, examples of potentially abuse related AE terms that meet the criteria for ESAM reporting, and guidance for the training of investigators and trial site staff.

8.8.7 Potential Serious Hepatotoxicity

For a subject who experiences an elevation in aspartate aminotransferase (AST) or alanine aminotransferase (ALT) that is ≥ 3 times the upper limit of normal (ULN), a total bilirubin level should also be evaluated. If the total bilirubin is ≥ 2 times the ULN, complete an IRE form with all values listed and also report as an AE in the eCRF.

8.8.8 Procedure for Breaking the Blind

The investigator is encouraged to contact the sponsor's designated medical advisor to discuss their rationale for unblinding. However, to prevent delays to the investigator or medical personnel responding to a potentially emergent situation, unblinding of IMP will not be dependent upon the investigator receiving approval from the sponsor's designated medical advisor (ie, the investigator will be able to obtain the code break information independent of the sponsor's designated medical advisor). The investigator must contact the sponsor's designated medical advisor by telephone or e-mail with an explanation of the need for opening the treatment assignment code within 24 hours of opening the code. If the blind is broken, the Global Pharmacovigilance Department must be notified immediately (see the cover page of this protocol for contact information). Documentation of breaking the blind should be recorded in the subject's medical record with the date and time the blind was broken and the names of the personnel involved. Once the blind is broken for a subject, that subject may not reinitiate treatment with the IMP.

8.8.9 Follow-up of Adverse Events

8.8.9.1 Follow-up of Nonserious Adverse Events

Nonserious AEs that are identified at any time during the trial must be recorded on the AE eCRF with the current status (ongoing or resolved/recovered) noted. All nonserious events (that are not IREs) that are ongoing at the last scheduled contact will be recorded as ongoing in the eCRF. For any AE having been identified throughout the trial, during analysis, additional relevant medical history information may be requested by the sponsor to further ascertain causality (including, but not limited to, information such as risk-related behavior, family history, and occupation).

8.8.9.2 Follow-up of Immediately Reportable Events

This trial requires that subjects be actively monitored for IREs up to 30 days after the last dose of IMP is administered.

Immediately reportable events that are **identified or ongoing at the last scheduled contact** must be recorded as such on the AE eCRF page and the IRE form. If updated information (eg, resolved status) on IRE status becomes available after a subject's last

scheduled contact (up to last in-clinic visit for the entire trial), this must be reported to the sponsor and recorded on the AE eCRF page and the IRE form, according to the appropriate reporting procedures described in Section 8.8.3.

It is expected that the investigator will provide or arrange appropriate supportive care for the subject and will provide prompt updates on the subject's status to the sponsor. The investigator will follow IREs until the events are:

- Resolved,
- Stabilized,
- The subject is lost to follow-up, or
- Has died.

Resolution means that the subject has returned to the baseline state of health and stabilized means that the investigator does not expect any further improvement or worsening of the subject's condition. The investigator will continue to report any significant follow-up information to the sponsor up to the point the event has resolved or stabilized, or the subject is lost to follow-up, or has died.

Refer to Section 10.3 for additional information regarding the follow-up period for subjects that become pregnant or for pregnant partners of male subjects.

8.8.9.3 Follow-up and Reporting of Immediately Reportable Events **Occurring After Last Scheduled Contact**

Any new IREs reported to the investigator which occur after the last scheduled contact and are determined by the investigator to be reasonably associated with the use of the IMP, should be reported to the sponsor according to the procedures outlined in Section 8.8.3. This may include IREs that are captured on follow-up telephone contact or at any other time point after the defined trial period and continue to report any significant follow-up information to the sponsor until the events are resolved or stabilized, or the subject is lost to follow-up or has died.

8.9 **Treatment of Overdose**

For treatment of overdose, refer to the IB. 15

8.10 Subject Assessment Recording

8.10.1 Diagnostic Criteria for Binge Eating Disorder

The subject's DSM-5⁷ diagnosis of BED, based on the clinical interview and medical/psychiatric history and confirmed by the SCID-5-CT, should be documented in eSource.

8.10.2 Structured Clinical Interview for DSM-5

The SCID-5-CT is a primary diagnostic measure that will be utilized to establish the presence of binge eating disorder in adults.

8.11 Other Assessments

Not applicable.

9 Statistical Considerations

9.1 Sample Size

Assuming a treatment difference of 1.1 points with a standard deviation of 1.7 in the mean change from baseline in binge eating days per week at Weeks 7-8 in either centanafadine dose group (high dose centanafadine or low dose centanafadine) compared to the placebo group (effect size = 0.65), a sample size of 114 evaluable subjects (38 in each treatment arm) will yield at least 80% power to detect the treatment effects at a 2-tailed significance level of 0.05. Approximately 126 subjects will be randomized to ensure 114 evaluable subjects in the study. The power and sample size were obtained using the PASS 14 (2015) statistical computing software.

9.2 **Datasets for Analysis**

The following datasets are defined for this trial:

[figure not shown]
- Randomized Analysis Set: comprises all subjects who were randomized in the double-blind treatment period. Subjects are considered randomized when they are assigned a treatment group at the baseline visit.
- Safety Analysis Set: comprises those randomized subjects in the double-blind treatment period who receive at least 1 dose of double-blind IMP. Subjects will only be excluded from this population if there is documented evidence (ie, numbers of drug dispensed are equal to numbers of drug returned, or no IMP dispensed at all) that the subject did not take IMP. If a subject is dispensed IMP and is lost to follow-up, he/she will be considered exposed.

• Efficacy Analysis Set: comprises all subjects in the Safety Analysis Set who have a baseline value and at least 1 valid post-randomization efficacy evaluation in the double-blind treatment period.

The core dataset for all efficacy analyses is the Efficacy Analysis Set. In order to handle missing data and restrictions imposed by different types of analyses (eg, change from baseline analysis), datasets derived from Efficacy Analysis Set will be used for the efficacy analysis.

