Statistical Methods: Assuming a treatment difference of 1.1 points with a standard deviation of 1.7 in the mean change from baseline in binge eating days per week at Weeks 7-8 in either centanafadine dose group (high dose centanafadine or low dose centanafadine) compared to the placebo group (effect size = 0.65), a sample size of 114 evaluable subjects (38 in each treatment arm) will yield at least 80% power to detect the treatment effects at a 2-tailed significance level of 0.05. Approximately 126 subjects will be randomized (42 in each treatment arm) to ensure 114 evaluable subjects in the study. The primary efficacy analysis will be performed by fitting a mixed-effect model repeated measures (MMRM) analysis with an unstructured variance covariance structure, in which change from baseline in binge eating days per week at the scheduled visits will be the dependent variable based on the observed cases (OC) data set. The model will

include fixed effect terms for treatment, trial center, visit week, and an interaction term of treatment by visit week. The model will also include the interaction term of baseline values of binge eating days per week by visit week as covariates. The primary comparison between centanafadine groups and the placebo group at Weeks 7-8 will be estimated as the difference between Least Squares means utilizing the computing software SAS procedure PROC MIXED. If there is a convergence problem with the unstructured variance covariance matrix of the MMRM model, the following structures other than unstructured will be used in order of 1) heterogeneous toeplitz, 2) heterogeneous autoregressive of order 1, and 3) heterogeneous compound symmetry and the first (co)variance structure converging to the best fit will be used as the primary analysis. If a structured covariance has to be used, the "sandwich" estimator of the standard error of the fixed effects parameters will be used in order to deal with possible model misspecification of the covariance matrix.

[figure not shown]
Trial Duration:

The anticipated duration for each participant to complete the trial is up to 13 weeks, which will include the following periods:

- Screening period: up to 4 weeks (28 days)
- Double-blind treatment period: 8 weeks
- Follow-up period: 7 (+ 2) days

Overall, the trial duration from signing of the first informed consent form to the final subject assessment is expected to be approximately 10 months.

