9.4 Statistical Analyses

9.4.1 Efficacy Analyses

9.4.1.1 Primary Efficacy Endpoint Analysis

The primary efficacy endpoint is the change from baseline in binge eating days per week at Weeks 7-8, having binge eating day defined as a day with at least one binge eating episode. The primary estimand defining the treatment effect of interest in the trial uses

Until the information herein is released by Otsuka to the public domain, the contents of this document are Otsuka

the hypothetical strategy specified in the draft ICH E9 (R1) Addendum.³⁷ In the hypothetical strategy, the event of withdrawing IMP is considered missing at random (MAR), and the primary endpoint of the trial could be considered as a combination of the responses of on-treatment completers at Week 8 and the imputation of the endpoint to Week 8 following the trend in each treatment group using the MMRM method for subjects who withdraw IMP during the trial. All data collected during the trial treatment period will be used for statistical analysis.

The comparison between the centanafadine groups and the placebo group will be tested at a significance level of 0.05 (2-sided) in a fixed sequence testing of 1) high dose centanafadine versus placebo, and 2) low dose centanafadine versus placebo, in which Test 2) won't be performed unless Test 1) is statistically significant.

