9.4.1.4 Other Efficacy Endpoint Analysis

Changes from baseline in Y-BOCS-BE score, PGI-S score, and SF-36v2 PCS and MCS scores will be analyzed using MMRM similar to primary efficacy endpoint. CGI-C score and PGI-C score will be analyzed using Cochran-Mantel-Haenszel (CMH) method based on raw mean score statistics with trial center as controlling factor. Proportion of subjects with four-week cessation from binging at Week 8/ET will be evaluated by the CMH method controlling for trial center. Change from baseline in EDE-Q7 global score will be

analyzed using analysis of covariance including treatment group, trial center as fixed factors and baseline as covariate. The other efficacy variables will be evaluated at a nominal 0.05 level (2-sided) without adjusting for multiplicity.

9.4.1.5 **Control of Experiment-wise Type 1 Error**

To control the overall experiment-wise type I error at the 0.05 level, a fixed sequence testing approach will be applied. The statistical test will be performed in the following order:

- 1) Change from baseline to Weeks 7-8 in binge eating days per week between high dose centanafadine and placebo;
- 2) Change from baseline to Weeks 7-8 in binge eating days per week between low dose centanafadine and placebo;
- 3) Change from baseline to Week 8 in CGI-S score between high dose centanafadine and placebo;
- 4) Change from baseline to Week 8 in CGI-S score between low dose centanafadine and placebo.

The test for the subsequent hypothesis will be performed only if the test for the previous hypothesis is statistically significant.

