3.3 Trial Population

Subjects are 18 to 65 years of age (inclusive), with a primary diagnosis of BED of at least moderate severity, with a history of at least 2 binge eating days per week for 6 months prior to screening and at least 3 binge eating days in each week during the previous 14 days of a subject's screening period according to the subject's binge diary as reviewed at baseline, a rating of 4 or higher on the Clinical Global Impression - Severity (CGI-S) at screening and baseline, and a body mass index (BMI) of 18 to 45 kg/m², inclusive. Subjects with a lifetime history or current diagnosis of bulimia nervosa or anorexia nervosa are excluded.

Approximately 228 adult subjects with BED are anticipated to be screened with the expectation that approximately 126 eligible subjects are to be randomized (42 subjects per treatment arm). The randomization is stratified by trial site.

4 Sample Size

Assuming a treatment difference of 1.1 points with a standard deviation of 1.7 in the mean change from baseline in binge eating days per week at Weeks 7-8 in either centanafadine dose group (high dose centanafadine or low dose centanafadine) compared to the placebo group (effect size = 0.65), a sample size of 114 evaluable subjects (38 in each treatment arm) yield at least 80% power to detect the treatment effects at a 2-tailed significance level of 0.05. Approximately 126 subjects are randomized to ensure 114 evaluable subjects in the study. The power and sample size were obtained using the PASS 14 (2015) statistical computing software.

5 Statistical Analysis Datasets

The following datasets are defined for this trial:

- Randomized Analysis Set comprises all subjects who are randomized in the double-blind treatment period. Subjects are considered randomized subjects when they are assigned a treatment group at the baseline visit.
- Safety Analysis Set comprises those randomized subjects in the double-blind treatment period who receive at least 1 dose of double-blind IMP. Subjects will only be excluded from this population if there is documented evidence (ie, numbers of drug dispensed are equal to numbers of drug returned, or no IMP dispensed at all) that the subject did not take IMP. If a subject is dispensed IMP and is lost to follow-up, he/she is considered as exposure to IMP.

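### The stated 80% power is for a single comparison; under the fixed sequence the low dose has about 68–69% on the plan's own inputs, and neither document says so.

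*Protocol*

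**What the plan says.** The sample size rationale appears in Protocol 1.1 (Statistical Methods), Protocol 9.1 and SAP section 4, in nearly the same words. It begins "Assuming a treatment difference of 1.1 points with a standard deviation of 1.7 in the mean change from baseline in binge eating days per week" and places that difference "in either centanafadine dose group (high dose centanafadine or low dose centanafadine) compared to the placebo group", with an effect size given as 0.65. It concludes that "a sample size of 114 evaluable subjects (38 in each treatment arm) will yield at least 80% power to detect the treatment effects" at a two-sided 0.05 level. The SAP repeats this: "a sample size of 114 evaluable subjects (38 in each treatment arm) yield at least 80% power to detect the treatment effects". The plan randomizes 126 subjects (42 per arm) to obtain the 114 evaluable.

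The testing procedure is described elsewhere. Protocol 9.4.1.1 and SAP 8.2.1 test high dose versus placebo first, then low dose versus placebo, "in which Test 2) won't be performed unless Test 1) is statistically significant". Protocol 9.4.1.5 and SAP 8.4 extend the sequence to CGI-S for each dose and restate the gate: "The test for the subsequent hypothesis will be performed only if the test for the previous hypothesis is statistically significant".

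The sample size text does not mention the sequence, and the sequence text does not mention power. Nothing in either document calls the 80% a per-comparison figure or gives the low-dose power under the sequence.

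**The concern.** The primary objective covers both doses, and low dose versus placebo is the second of the two primary comparisons. Someone reading the sample size section would take 80% as the chance that a true 1.1-day low-dose effect is declared significant, and so put the chance of missing it at about 1 in 5. Under the planned procedure the low dose can be declared significant only when the high dose is too, so the chance of missing it must be larger.

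This matters most when the results are read. A low-dose effect that is not declared significant, or never formally tested, carries less evidence against that dose if the procedure had about 69% power than if it had 80%.

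**Working it through.** **Inputs.** Difference 1.1 for each dose, SD 1.7, 38 evaluable per arm and two-sided alpha 0.05 (Protocol 9.1, SAP 4); 1:1:1 allocation (Protocol 6.3); low dose gated on high dose (Protocol 9.4.1.1 and 9.4.1.5, SAP 8.2.1 and 8.4).

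**Step 1: reproduce the stated figure.**

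- Effect size: 1.1 / 1.7 = 0.647, given in the plan as 0.65.
- Standard error of one difference: 1.7 × √(2/38) = 0.390.
- Expected z: 1.1 / 0.390 = 2.82.
- Power by the normal approximation: Φ(2.82 − 1.96) = Φ(0.86) = 80.5%.
- Power by the noncentral t with 74 df: 79.5%.

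The stated 80% is therefore the power of one dose-versus-placebo comparison.

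**Step 2: low-dose power under the sequence.** The low dose is declared significant only if both tests succeed:

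P(low dose declared) = P(Z_high > 1.96 and Z_low > 1.96)

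The two differences share the placebo arm. With equal arms their covariance is SD²/n and each variance is 2·SD²/n, so the correlation is 0.5. Both expected z values are 2.82.

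- Bivariate normal: 69.4%.
- Simulated two-arm t-tests (1,000,000 replicates): 68.1%.
- Simulated t-tests with three-arm pooled variance: 68.6%.

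**Step 3: where the loss arises** (two-arm t-tests, both differences 1.1).

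| Outcome for the low dose | Share of trials |
|---|---|
| Not tested, because the high dose was not significant | 20.4% |
| Tested and not significant | 11.5% |
| Declared significant | 68.1% |

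Once tested, the low dose is declared significant in 0.681 / 0.796 = 85.5% of trials. Most of the shortfall comes from the gate.

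**Step 4: sensitivity.** SD is 1.7 except in the last two rows. Effects other than 1.1, and the baseline–change correlations r, are assumptions; the documents do not give them. The adjusted SD is 1.7 × √(1 − r²).

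| High / low effect | n per arm | Condition | Bivariate normal | Simulated t |
|---|---|---|---|---|
| 1.1 / 1.1 | 38 | plan's inputs | 69.4% | 68.1% |
| 1.1 / 1.1 | 42 | all randomized subjects evaluable | 74.7% | 73.5% |
| 1.3 / 1.1 | 38 | | 76.5% | 75.2% |
| 1.4 / 1.1 | 38 | | 78.3% | 77.1% |
| 1.5 / 1.1 | 38 | | 79.4% | 78.3% |
| 0.9 / 1.1 | 38 | | 56.9% | 55.5% |
| 1.1 / 0.8 | 38 | | 48.8% | 47.7% |
| 1.1 / 1.1 | 38 | r = 0.3, SD 1.622 | 74.4% | 73.1% |
| 1.1 / 1.1 | 38 | r = 0.45, SD 1.518 | 80.9% | 79.7% |

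For scale only: about 47 (normal) to 48 (t) evaluable subjects per arm would be needed for 80% low-dose power under the sequence at the plan's inputs.

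**The case against.** The strongest reply is that nothing has been miscalculated. One difference, one SD and a two-sided 0.05 level are plainly the inputs of a single two-group comparison. Grammatically, the reference to either dose qualifies the assumed difference and not the power. Powering each comparison separately and then ordering the tests is a legitimate choice in a phase 2 proof-of-concept trial. The sequence is fully disclosed, no target is set for both doses to succeed, and a statistical reader can work out the consequence. All of this is fair. It makes the point one of labelling, but the label is still missing for a comparison that the plan tests only conditionally.

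A second reply is that 68–69% is one scenario. It needs both effects to be 1.1 and takes no credit for the baseline covariate in the MMRM; an assumed correlation of 0.45 would bring the low dose back to about 80%. The equal-effects scenario is, however, the plan's own sizing assumption. The documents do not say whether 1.7 is already adjusted and give no correlation. The same precision gain would also lift the high dose to about 88% (normal approximation), so the gap between the two doses would remain.

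A third reply is that 38 per arm reaches 80% only by the normal approximation, so a corrected sentence should not mix methods. That is right, and the wording proposed below uses one method. The difference between methods is about one point, against a shortfall of about 11.

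**Conclusion.** The concern holds. The 80% is correct as per-comparison power and stands for high dose versus placebo. For low dose versus placebo, the planned procedure gives 68–69% at the plan's own inputs, so the chance of missing a true 1.1-day effect is nearly 1 in 3. Even if all 42 subjects per arm were evaluable, the figure would be 74–75%.

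These figures assume equal true differences of 1.1, SD 1.7 and no precision gain from covariates. The low-dose figure rises towards the pairwise value if the high-dose effect is larger, and falls if either effect is smaller. The fault lies in the power statement for one of the two primary comparisons. It does not affect type I error, the estimates or the decision rule.

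**What to change.** Leave the sample size and the testing order as they are. In Protocol 1.1, Protocol 9.1 and SAP section 4, label the 80% and add the sequence figure, with both computed by one named method. For example:

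> By the normal approximation, 38 evaluable subjects per arm give 80% power for a single dose-versus-placebo comparison. This applies to high dose versus placebo, which is tested first. Under the fixed-sequence procedure, the probability of declaring low dose versus placebo significant is about 69% if both true differences are 1.1 with SD 1.7, with no credit for covariate adjustment in the MMRM. It is higher if the high-dose effect is larger and lower if either effect is smaller.

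If the sponsor prefers t-based figures, the matching pair is 79.5% and 68.1%, and the claim of at least 80% would then need softening. It would also help to state whether the SD of 1.7 is already adjusted for baseline.

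The cost is wording in three places and a less favourable figure shown for the low dose. No subjects, tests or analyses change.
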